## 7.5.4 Sensitivity Analyses

A number of sensitivity analyses are planned to evaluate the robustness of the primary and secondary efficacy results.

For the primary efficacy endpoint, the following sensitivity analyses will be performed:

- Analysis of primary efficacy endpoint using the PP Analysis Set.
- Analysis of primary efficacy endpoint using the specified MMRM model but including additional covariates of race, smoking, age, and Fitzpatrick skin type as model convergence allows.
- Multiple imputation with FCS method (described below).
- Tipping point analysis (described below).
- Prior to database lock and unblinding, the assumption of normality in the change from baseline in AN count will be checked by visually inspecting the distribution of the residuals. If the normality assumption is not met, a repeated-measure GEE approach with an appropriate distribution (e.g. logarithm or generalized logit transformation) will be considered. An unstructured correlation matrix will be used in the model if GEE is decided to be used. However, the results from the primary efficacy analysis will be considered the primary efficacy results.

### Multiple Imputation with Fully Conditional Specification (FCS) Method

The FCS method can be used to impute missing values for variables with an arbitrary missing data pattern, assuming the existence of a joint distribution for these variables. Both intermittent and monotone missing AN values will be imputed in the same way with a regression-based predictive mean matching method. The missing values will be imputed sequentially, with all previous visits included as additional covariates.

The steps of performing a sequential regression imputation are as follows:

- a) If there is any missing value at Week 4, it will be imputed using a regression-based predictive mean matching method. A randomization seed of 20225678 will be used. For AN counts, the regression will include the covariates age, treatment group, race, gender, Hurley Stage at baseline (Stage II vs. III), and the baseline measurement of AN counts.
- b) All remaining missing visits will be imputed sequentially by the same regression, with covariates specified above in Step (a) and the values (including the imputed values) from earlier visits.
- c) For the final Week 16 imputed values, the imputed values will be rounded to the nearest integer for AN count. For intermediate imputed values, the exact values will be kept for the purpose of imputation for the next visit.

The linear mixed model for repeated measures (MMRM) for continuous endpoints as described in **Section 7.5.1** will be applied to each imputed dataset. At least one hundred independent data replications will be done with SAS PROC MI. Results across the replicated datasets will then be combined into the final estimate using SAS PROC MIANALYZE.

### Tipping Point Analyses

The following steps will be used to determine the tipping point:

- a) Intermittent missing values will be imputed using the Monte Carlo Markov Chain (MCMC) approach to create a monotone missing pattern. The imputation will be implemented separately for each treatment and each Hurley Stage at baseline (Stage II or III), under the assumption that

different treatments may have distinct posterior distributions. The imputation will include the all post-baseline values, with age, race, gender, Fitzpatrick skin type, and baseline value of the corresponding endpoint as covariates.

- b) If there is any missing value at timepoint 1 (Week 4), it will be imputed using a regression based MI method for monotone missingness. Covariates included in the modelling are age, race, gender, Fitzpatrick skin type, and baseline value of the corresponding endpoint.
- c) A delta score will be added to the imputed value at timepoint 1 for subjects missing data at timepoint 1 in the imsidolimab treatment groups, thus worsening the imputed value. The delta value will start at 0 and will be increased in a repeated process until the comparison of imsidolimab to placebo is no longer significant at 0.10 level in step (f).
- d) All remaining timepoints will be imputed sequentially by repeating Steps (b) and (c) for each timepoint, including values from earlier timepoints in the imputation model, which include imputed values from the previous step, in addition to the covariates specified above in Step (b). Data from subjects who have already had their responses increased by delta in the previous step(s) will not be further increased by delta again since the regression on the previous value carries this increase forward. This principle also extends to the preliminary step of imputing intermittently missing visits. Thus, if an intermittent missing value is encountered for a subject in the imsidolimab treatment groups, delta adjustment will not apply for the subsequent imputations of the monotone part of the missing visits, for that subject.
- e) For each imputed dataset, perform the same primary analysis (MMRM) as described in **Section 7.5.1** to estimate treatment differences between each dose of imsidolimab and placebo. Results across the imputed datasets will then be combined using SAS PROC MIANALYZE.
- f) Step (c) to (e) will be repeated with gradually increased delta values until the tipping point is reached.

At least one hundred (100) independent dataset replications will be done with SAS PROC MI. The resulting 100 estimates of the treatment differences and standard errors will then be combined into the final estimate using SAS PROC MIANALYZE.

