### 9.2 SAMPLE SIZE DETERMINATION

Approximately 120 subjects will be randomized in a 1:1:1 ratio to receive one of the following study treatments:

1. Imsidolimab 400 mg on Day 1 followed by 200 mg on Days 29, 57, and 85
2. Imsidolimab 200 mg on Day 1, followed by 100 mg on Days 29, 57, and 85
3. Placebo on Days 1, 29, 57, and 85

For this phase 2 study, the sample size was chosen empirically. Assuming a total of 10% of subjects will discontinue prior to Week 16, there will be approximately 108 evaluable subjects (36 subjects in each arm) at the end of Week 16. The study has 80% power to detect a between-group treatment difference of 4.9 lesions in the primary endpoint of mean change from Baseline in the AN count at Week 16, using a two-sided, equal-variance two-sample t-test at the  $\alpha = 0.10$  level, with the assumption of a common standard deviation (SD) of 8.2 lesions. The assumption was based on PIONEER 1 study (Kimball 2016). Table 6 shows more information on power from a set of scenarios of variability and between-group mean differences.

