### 3.3 Hypothesis Testing

The primary analysis for this study is to compare the mean change from baseline in AN count for imsidolimab vs. placebo at Week 16 of the double-blind treatment period, at a two-sided alpha = 0.10 level. The following hypothesis test will be done separately for each imsidolimab dose arm.

$$H_0: \mu_{\text{imsidolimab}} - \mu_{\text{placebo}} = 0 \text{ vs. } H_A: \mu_{\text{imsidolimab}} - \mu_{\text{placebo}} \neq 0$$

Treatment comparisons may be performed for the secondary or exploratory endpoints and will be considered exploratory in nature. Two-sided p-values and 90% confidence intervals will be produced.

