### 7.1.2 Tipping Point Analyses

As the primary analysis (mixed effects model for repeated measures [MMRM]) relies on the missing at random (MAR) assumption, to evaluate the robustness of the primary analysis approach, a sensitivity analysis using the tipping-point approach will be conducted. This analysis is described in **Section 7.5.4**.

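### SAP 7.5.4: the tipping-point regressions for dropouts do not name treatment arm, so as written an effective drug's delta = 0 estimate is already shrunk and the tipping delta is not a distance from MAR

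*SAP*

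**What the plan says.** SAP 7.1.2 gives the purpose. The primary MMRM relies on data being missing at random (MAR), so "to evaluate the robustness of the primary analysis approach, a sensitivity analysis using the tipping-point approach will be conducted".

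The procedure is in SAP 7.5.4, Tipping Point Analyses:

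- Step (a) fills intermittent gaps only, by MCMC. "The imputation will be implemented separately for each treatment and each Hurley Stage at baseline (Stage II or III), under the assumption that" the treatments may differ in their posterior distributions.
- Step (b) imputes missing Week 4 values in the now monotone pattern by regression. "Covariates included in the modelling are age, race, gender, Fitzpatrick skin type, and baseline value of the corresponding endpoint".
- Step (c) adds delta to the imputed imsidolimab values only, starting from 0.
- Step (d) repeats (b) and (c) visit by visit, adding earlier values to the step (b) covariates.
- Step (e) applies the primary MMRM, which by SAP 7.5.1 contains treatment, treatment by visit, Hurley stage and baseline AN count.

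For the FCS imputation in the same section, "the regression will include the covariates age, treatment group, race, gender, Hurley Stage at baseline" and the baseline AN count. In Appendix 2 the BY statement on Hurley stage and treatment stands only in the MCMC call for intermittent gaps. There is no code for the monotone step.

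**The concern.** A tipping-point analysis reports how far the dropouts must depart from MAR before significance is lost. That reading needs a starting point, delta = 0, which approximates the MAR result. If the dropout regressions do not contain treatment, missing values in every arm are drawn from a model fitted to all three arms together. The imputed values then lie closer together than the observed ones, and the treatment difference shrinks before any delta is added. A result that is significant in the MMRM could then be non-significant at delta = 0, and the reported delta would mix the intended departure with an effect of the imputation model.

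**Working it through.** **Inputs.** Protocol 9.2: "Approximately 120 subjects will be randomized in a 1:1:1 ratio", so 40 per arm. The 10% expected loss before Week 16 leaves 40 × 0.9 = 36. "The study has 80% power to detect a between-group treatment difference of 4.9 lesions", "with the assumption of a common standard deviation (SD) of 8.2 lesions". SAP 3.3: each dose is tested against placebo "at a two-sided alpha = 0.10 level".

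**1. The plan's own figure.** SE = 8.2 × √(2/36) = 1.933, and 4.9 / 1.933 = 2.535. The normal approximation gives power Φ(2.535 − 1.645) = 81.3%; the noncentral t on 70 degrees of freedom gives 80.7%. The stated 80% reproduces. The documents give no figure for the tipping-point analysis itself.

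**2. Upper bound by hand.** Let a fraction d of each arm leave before Week 4, so that nothing observed after baseline carries treatment information. A pooled regression then draws every missing value around the pooled mean. With 1:1:1 allocation and two equally active doses, that mean lies two thirds of the way from placebo to active.

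- Each imputed imsidolimab value moves 4.9 / 3 = 1.63 lesions towards placebo.
- Each imputed placebo value moves 2 × 4.9 / 3 = 3.27 lesions towards active.
- Loss = d × (1.63 + 3.27) = 0.10 × 4.9 = 0.49 lesions, or 0.49 / 1.93 = 0.25 standard errors.

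The two shifts add up to the full effect wherever the pooled mean lies, so the bound does not need equal doses. The placebo part, 0.10 × 3.27 = 0.33 of the 0.49, has no counterpart in delta, which is added to imsidolimab values only. Subjects who leave later keep earlier AN counts that carry part of the effect, so their shrinkage is smaller.

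**3. Size of the shrinkage.** Simulation with 150,000 per arm, true difference −4.9, sequential regression imputation at delta = 0, then ANCOVA at Week 16 with treatment, Hurley stage and baseline. Estimates under the written covariate list, over visit correlations 0.3 to 0.7:

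| Missing | Spread over four visits | All before Week 4 | Late (Weeks 12 and 16) |
|---|---|---|---|
| 10% | −4.52 to −4.58 (6% to 8%) | −4.42 to −4.45 (10%) | −4.61 to −4.72 (4% to 6%) |
| 20% | −4.15 to −4.30 (13% to 15%) | −3.86 to −3.90 (about 20%) | −4.28 to −4.47 (8% to 12%) |
| 30% | −3.81 to −3.99 (18% to 23%) | −3.37 to −3.46 (about 30%) | −4.06 to −4.26 (12% to 18%) |

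With treatment and Hurley stage in the imputation model, the estimates are −4.84 to −4.97. Further checks, with missingness spread over the visits and correlation 0.5:

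- Only the higher dose active, 10% missing: −4.62 written, −4.94 with both terms.
- No true effect, 20% missing: 0.03 and 0.05, so no shrinkage.
- Treatment in, Hurley stage out, 20% missing: −4.90, against −4.88 with both terms and −4.24 with neither.

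A separate simulation under other assumptions (effect building from 2.0 lesions at Week 4, adjacent-visit correlation 0.65, 700 trials per scenario) gave 7% for 10% dropout spread over the visits, 10% if all left before Week 4, and 12% at 20% missing.

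**4. At the planned size.** 40 per arm, correlation 0.5, missingness spread over the visits, 800 trials, 20 imputations combined by Rubin's rules. Each cell gives the written list first, then the list with treatment and Hurley stage:

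| Missing | Mean estimate | Significant at delta = 0 | Significant only with both terms | Significant only as written |
|---|---|---|---|---|
| 10% | −4.56 / −4.90 | 77% / 80% | 4% | 0.4% |
| 20% | −4.19 / −4.84 | 67% / 75% | 8% | 0.5% |
| 30% | −3.86 / −4.87 | 57% / 70% | 14% | 0.5% |

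**The case against.** The strongest reply is that by-arm processing was meant to carry over. Steps (a) and (b) name the same covariates. In (a), treatment and Hurley stage are missing from the list because they define the groups, and the reason given there, that treatments may differ, applies just as well to dropouts. Appendix 2 describes itself as still to be completed, so its silence proves little. This stands as a plausible account of intent. It is not what the text says: the by-arm sentence sits inside the step for intermittent gaps, and (b) and (d) give their own explicit list. A programmer following that list would pool the arms.

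The reply that the consequence is limited also stands. This is one of several sensitivity analyses, the error is conservative, and it cannot make a fragile result look robust.

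Three stronger readings are tempting, and the documents do not support them:

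- A reader might infer that omitting Hurley stage also causes the shrinkage. The check above shows almost no effect.
- A reader might infer that delta = 0 is a non-MAR scenario of unknown size. No missingness mechanism is specified as non-MAR. The fault is an imputation model that does not match the MMRM, and its effect is bounded by about dropout × effect.
- A reader might infer that delta = 0 should reproduce the FCS or MMRM estimate. The FCS step uses predictive mean matching, rounds Week 16 values and has no Fitzpatrick term. The MMRM has no age, race, gender or skin type. Comparison is reasonable; exact agreement is not.

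**Conclusion.** The point holds for steps (b) and (d) as written. If the drug works, the delta = 0 estimate is shrunk by about 4% to 10% at the planned 10% dropout, and the tipping delta comes out too small to be read as a departure from MAR. The loss is modest at that rate. It grows with missingness, and SAP 7.5.1 adds to missingness by setting post-rescue data to missing. Protocol 6.6 allows rescue only from Week 8, so that source falls in the later visits, where the shrinkage per missing value is smaller.

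The primary MMRM and the FCS analysis are unaffected. Hurley stage is a matter of consistency with step (a) and the MMRM.

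The sizes rest on assumptions that the documents do not give: visit correlations of 0.3 to 0.7, an effect reaching 50%, 75%, 90% and 100% of its final size over the four visits, a Hurley effect of 3 lesions with 40% in Stage III, dropout completely at random, and the 20% and 30% missingness rates. The direction and the bound do not depend on the correlation.

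**What to change.** State in steps (b) and (d) that the regressions include treatment arm, or are run separately by arm, and that they include Hurley stage at baseline. Splitting fully by arm and stage would leave cells of 120 / 6 = 20 subjects on average, so adding the terms as covariates is likely to be the more stable choice. Add the monotone PROC MI code to Appendix 2, which has none for this step. Report the delta = 0 result beside the primary MMRM estimate and explain any marked difference, without requiring exact agreement.

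The cost is about one line of SAP text and one short block of code. No data collection or primary analysis changes. If by-arm processing was always intended, the same line serves as the clarification.

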### **3.5 Sample Size**

The primary efficacy endpoint is the change from baseline in AN count at Week 16. The null hypothesis ( $H_0$ ) to be tested is that the mean change from baseline in AN count is the same for imsidolimab and placebo. This will be tested separately for each imsidolimab dose arm. Assuming a common standard deviation (SD) of 8.2, and a 10% dropout rate, an enrollment of 40 subjects (leaving 36 after dropout) in each of imsidolimab treatment arms and 40 subjects (leaving 36 after dropout) in the placebo arm will have at least 80% power to detect the overall treatment effect for a two sample t-test using a 2-sided significance level of  $\alpha=0.10$ , where the difference in the mean change from baseline between the imsidolimab and placebo group is assumed to be 4.9. The common standard deviation assumption was based on the PIONEER 1 study (Kimball 2014). No adjustments to  $\alpha$  are needed in this study for primary analysis or multiple comparisons.

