## APPENDIX 2 SAS CODE FOR STATISTICAL ANALYSES

This section will be completed after examining the existing data and prior to the final signoff of this SAP.

Test	Template SAS Code for Modeling (SAS Version 9.4)
Linear Repeated Measures Analysis of Covariance for the primary endpoint	<pre> PROC MIXED METHOD=REML;   CLASS SUBJECT TRT VISIT BASEHSSTAGE;   MODEL Y = BASE TRT VISIT TRT VISIT/ DDFM=KR SOLUTION   OUTP=OUT;   REPEATED VISIT / TYPE = UN SUBJECT = SUBJECT;   LSMEANS TRT VISIT / PDIFF CL ALPHA=0.1;   ODS OUTPUT LSMEANS=MEANS;   ODS OUTPUT DIFFS=DIFF;   RUN; </pre> 
Where TRT is treatment, VISIT is the study visit number, BASEHSSTAGE is the baseline Hurley Stage, and BASE is the baseline of outcome variable.

General Estimating Equation Repeated Measures with Generalized Logit Transformation	<pre> PROC GENMOD;   CLASS SUBJECT TRT VISIT BASEHSSTAGE;   MODEL Y= BASE TRT VISIT TRT*VISIT / LINK=LOGIT DIST=NEGBIN;   REPEATED SUBJECT=SUBJECT / TYPE=UN;   LSMEANS TRT VISIT / DIFF CL ALPHA=0.1;   ODS OUTPUT LSMEANDIFFS = LSDIFS ESTIMATES=EST   LSMEANS=LSMEANS PARAMETERESTIMATES=PE; </pre> 
Where TRT is treatment, VISIT is the study visit number, BASEHSSTAGE is the baseline Hurley Stage, and BASE is the baseline of outcome variable.

General Estimating Equation Repeated Measures for secondary and exploratory endpoints	<pre> PROC GENMOD;   CLASS SUBJECT TRT VISIT;   MODEL Y = TRT VISIT TRT*VISIT/ DIST=BIN LINK=LOGIT;   REPEATED SUBJECT = SUBJECT /TYPE=UN;   RUN; </pre> 
Where TRT is treatment and VISIT is the study visit number.

Test	Template SAS Code for Modeling (SAS Version 9.4)
Impute Intermittent Missing using the Monte Carlo Markov Chain (MCMC) approach	<pre> PROC MI DATA=data_in SEED=2330710 NIMPUTE=100 OUT=LESION_MONO;   BY BASEHSSTAGE TRT; /*Assuming different treatment, baseline Hurley Stage has different distribution*/   MCMC CHAIN=MULTIPLE IMPUTE=MONOTONE; /*Only impute intermittent missing values*/   VAR AGE BASE AN1 – AN5; /*Impute AN count from Week 4 to Week 16, with age and baseline as covariates*/   RUN; </pre>
Multiple Imputation with FCS Method	<pre> PROC MI MIN=0 ROUND=1;   CLASS BASEHSSTAGE TRT SEX;   FCS REGPMM(AN2 = AN1 AGE SEX TRT BASE BASEHSSTAGE );   FCS REGPMM(AN3 = AN1 AN2 AGE SEX TRT BASE BASEHSSTAGE );   FCS REGPMM(AN4 = AN1-AN3 AGE SEX TRT BASE BASEHSSTAGE );   FCS REGPMM(AN5 = AN1 AN4 AGE SEX TRT BASE BASEHSSTAGE );   VAR AN1 – AN5 AGE SEX TRT BASE BASEHSSTAGE;   RUN; </pre>

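### The tipping-point rule never worsens the missing Week 16 value of an imsidolimab subject who misses a visit, returns and then drops out, which inflates the tipping delta

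*SAP*

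**What the plan says.** SAP section 7.1.2 gives the purpose: because the primary MMRM relies on missing-at-random, "to evaluate the robustness of the primary analysis approach, a sensitivity analysis using the tipping-point approach will be conducted". The algorithm is in section 7.5.4.

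- **Step (a):** "Intermittent missing values will be imputed using the Monte Carlo Markov Chain (MCMC) approach to create a monotone missing pattern". No delta is mentioned. The matching Appendix 2 template, "MCMC CHAIN=MULTIPLE IMPUTE=MONOTONE; /*Only impute intermittent missing values", has none either.
- **Step (c):** "A delta score will be added to the imputed value at timepoint 1 for subjects missing data at timepoint 1", in the imsidolimab groups only. This is where delta first appears.
- **Step (d):** later visits are imputed in sequence by repeating (b) and (c). Subjects already shifted "will not be further increased by delta again since the regression on the previous value carries this increase forward". The step then applies the same principle to the gap-filling stage, so that "if an intermittent missing value is encountered for a subject in the imsidolimab treatment groups, delta adjustment will not apply for the subsequent imputations" of that subject's monotone-missing visits.
- **Step (f):** "Step (c) to (e) will be repeated with gradually increased delta values until the tipping point is reached". Step (a) lies outside the loop.

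**The concern.** The exemption rests on an increase that was never made. A subject whose monotone missingness began at Week 8 received delta there, so there is a reason not to add it again at Week 12. A subject with only an intermittent gap received none, because the gap was filled under missing-at-random and the loop over delta never returns to that step. There is no increase to carry forward.

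Taken literally, an imsidolimab subject who misses Week 8, attends Week 12 and is missing at Week 16 keeps a missing-at-random Week 16 value however large delta becomes. The reported tipping delta would be read as the amount by which all missing imsidolimab values must worsen before significance is lost, when it was applied to only some of them. At the planned level of missingness the error runs one way, towards apparent robustness.

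**Working it through.** **Inputs.** SAP 3.5 and Protocol 9.2 give 40 per arm with 36 remaining ("an enrollment of 40 subjects (leaving 36 after dropout) in each of imsidolimab treatment arms"), SD 8.2, design difference 4.9 and two-sided alpha 0.10. About 40 − 36 = 4 subjects per arm are thus missing at Week 16. The documents do not give k, the number of those four imsidolimab subjects with an earlier gap, so it is varied.

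**The plan's own figure.** A two-sample t-test with 36 per arm has noncentrality 4.9 / (8.2 × √(2/36)) = 2.535 and power 80.7%, which agrees with the stated 80%. The documents state no tipping delta.

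**Closed form.** Let D be the observed benefit, N = 40, m = 4 missing, j = m − k receiving delta, and f = j/40. If delta x reaches Week 16 in full, the tipping value solves

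(D − f·x) / √[(2 × 8.2² + f(1 − f)x²) / 40] = t(0.95; 78) = 1.665.

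For D = 4.9:

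- k = 0, f = 0.10, x = 15.97: (4.9 − 1.597) / √[(134.48 + 22.95)/40] = 3.303 / 1.984 = 1.665.
- k = 1, f = 0.075, x = 20.46: 3.366 / 2.022 = 1.665.
- k = 2, f = 0.05, x = 28.66: 3.467 / 2.083 = 1.665.

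**Simulation.** There were 300 data sets per scenario, with the completer difference fixed, 60 missing-at-random imputations and Rubin's rules. A two-sample comparison stands in for the MMRM. Tipping values are medians. They lie below the closed form, which treats all 40 per arm as observed and so omits imputation uncertainty.

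| D | Exempt of 4 | Closed form | Ratio to none exempt | Simulation |
|---|---|---|---|---|
| 4.0 | 0 | 8.7 | 1 | 7.0 |
| 4.0 | 1 | 11.3 | 1.30 | 9.2 |
| 4.0 | 2 | 16.2 | 1.86 | 13.3 |
| 4.9 | 0 | 16.0 | 1 | 14.5 |
| 4.9 | 1 | 20.5 | 1.28 | 18.7 |
| 4.9 | 2 | 28.7 | 1.79 | 26.2 |

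The simulated ratios are 1.28 to 1.31 with one exempt and 1.81 to 1.92 with two. If the SD did not grow with delta, the ratio would be m/(m − k), that is 4/3 = 1.33 and 4/2 = 2.0. Growth in the SD brings it slightly below that. With all four exempt no tipping point exists.

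**Steps (a) to (f) run directly.** A second simulation used 100 imputations, an observed difference of about 6, and gap subjects missing at Week 8, seen at Week 12 and missing at Week 16. With one gap subject, the mean imputed Week 16 change was −14.07 at delta 0 and −14.07 at delta 20. Giving that subject delta moved it to 5.93. The tipping delta was 23 to 24 when everyone received delta, against 29, 38 and 68 with one, two and three exempt. With four exempt it was not reached by 150.

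**Who can be exempt.** A gap must be followed by an attended visit, so monotone missingness must start at Week 12 or 16. If dropout starts are spread evenly over the four visits, that is 2 of 4, a maximum share of 50%.

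**A separate, smaller point.** Adding delta once, at the first missing visit, is a disclosed choice, but the shift that reaches Week 16 usually differs from the nominal delta. With constant SD, AR(1) correlation ρ and evenly spread dropout, the mean share carried is (1 + ρ + ρ² + ρ³)/4: 0.354 at ρ = 0.3 and 0.860 at ρ = 0.9. It can exceed 1 for some dropout visits if the SD rises steeply over time. The SAP does not plan to report the shift achieved.

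**The case against.** **The exempt subject may be rare.** Take one dropout starting at each visit and an independent chance p of missing any earlier visit, which the documents do not give. Three visits per arm could then produce a qualifying gap: one for the Week 12 starter and two for the Week 16 starter. The chance of at least one exempt subject per arm is 1 − (1 − p)³: 6%, 14% and 27% for p of 2%, 5% and 10%. The chance of two is p × [1 − (1 − p)²]: 0.1%, 0.5% and 1.9%. This stands, and the two-exempt figures are close to a worst case under even dropout.

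**The missing count is uncertain.** Post-rescue data are also set to missing (SAP 7.5.1). With 8 missing per arm and D = 4.9, one exemption moves the closed-form value only from 8.6 to 9.7, or 1.13-fold. However, Protocol 6.6 allows rescue only from Week 8, so this missingness starts late, when an earlier gap is possible. The 50% ceiling is therefore not firm either.

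**The reading may not change.** At 4.9 lesions, simulated tipping values of 14.5 and 18.7 are about 1.8 and 2.3 SDs, and both look robust. That is fair for one exemption at the design effect.

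**Delta may have been meant for the gap value.** Appendix 2 is an unfinished template with no delta step at any stage, so its silence is weak evidence, and step (d) could imply an unstated delta at gap filling. This does not rescue the rule. An observed visit lies between the gap and the dropout, so only 0% to about 32% of delta reaches Week 16 under AR(1) or exchangeable correlation. On that reading the direct simulation still gave 29, 39 and 64 with one, two and three gap subjects.

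**It is one of several sensitivity analyses in a Phase 2 study.** That limits the weight of the point but does not make the rule correct.

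**Conclusion.** The concern holds. Step (d) exempts a class of imsidolimab subjects for a reason that does not apply to them, and their missing Week 16 values are never worsened. Given a significant primary comparison and at least one imsidolimab subject with a gap followed by a missing Week 16 value, the tipping delta is overstated. With 4 missing per arm the overstatement is about 1.3-fold for one exempt subject and 1.8- to 1.9-fold for two.

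The direction follows from the text while fewer than half of an arm receives delta: fewer shifted subjects means both a smaller mean shift and a smaller rise in variance. The size rests on the assumed number exempt, 4 missing per arm, delta reaching Week 16 in full, and a two-sample stand-in for the MMRM. The primary estimate, its test and the power are unaffected. It should be corrected before the analysis is run, but it does not threaten the trial's main conclusion.

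**What to change.** Replace the last two sentences of step (d) with: *Every imsidolimab subject with monotone-missing data receives delta at the first monotone-missing visit, whether or not an earlier visit was intermittently missing.* Report how many imsidolimab subjects had a gap followed by dropout. It would also help, though the correction does not depend on it, to report the mean Week 16 shift achieved at the tipping delta.

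An alternative that also removes the carry-forward question is to reword steps (c), (d) and (f) together: complete all imputation under missing-at-random, add delta once to every missing imsidolimab Week 16 value, refit the primary MMRM, and repeat over delta. That is a different sensitivity analysis and is not needed to repair the inconsistency.

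The cost is SAP wording and a small code change, with no new data and no change to the primary analysis. The reported tipping delta will be smaller wherever such subjects exist, but it will then apply to every imsidolimab dropout.
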